18F-AV-1451-A18 Protocol

An Open Label, Multicenter Study Evaluating the Imaging Characteristics of a Follow up 18F-AV-1451 Scan in Subjects That Participated in the Confirmatory Cohort of 18F-AV-1451-A05

NCT02795780

Approval date: 22 Mar 2016

Protocol Number: ^{18}F -AV-1451-A18

An open label, multicenter study evaluating the imaging characteristics of a follow up ^{18}F -AV-1451 scan in subjects that participated in the confirmatory cohort of ^{18}F -AV-1451-A05

Date and Version:

22 March 2016, Final

Name of Compound:

^{18}F -AV-1451 ([F-18]T807)

Sponsor:

Avid Radiopharmaceuticals, Inc.
Philadelphia, Pennsylvania USA

Approval/Signature:

CONFIDENTIAL

This material is the property of Avid Radiopharmaceuticals, Inc. (Avid). The information is confidential and is to be used only in connection with matters authorized by Avid and no part of it is to be disclosed to others without prior written permission from Avid.

Sponsor: Avid Radiopharmaceuticals, Inc.	Name of Compound: ¹⁸ F-AV-1451([F-18]T807)	Active Ingredient(s): 7-(6-[F-18]fluoropyridin-3-yl)-5H-pyrido[4,3-b]indole
Title of Study: ¹⁸ F-AV-1451-A18 An open label, multicenter study evaluating the imaging characteristics of a follow up ¹⁸ F-AV-1451 scan in subjects that participated in the confirmatory cohort of ¹⁸ F-AV-1451-A05		
Planned number of subjects (Enrolled): Approximately 160		
Name of compound: ¹⁸ F-AV-1451(also known as [F-18]T807) Dose: 370 MBq (10 mCi) Route of Administration: Intravenous (IV) bolus		
Study Phase: II		
Study Centers: Approximately 25 centers in the United States		
Trial Objectives: The primary objective of this protocol is to assess longitudinal change of tau deposition as measured by ¹⁸ F-AV-1451 uptake over time.		
Eligibility: See Section 5.3, Selection of Subjects.		
Study Design: This is a phase 2 study that will evaluate longitudinal change of tau deposition as measured by ¹⁸ F-AV-1451 uptake over time. As subjects from the ¹⁸ F-AV-1451-A05 confirmatory cohort complete the ¹⁸ F-AV-1451-A05 study, they will be presented with the opportunity to participate in this longitudinal study. All subjects will provide informed consent before starting any study procedures. Screening assessments should take place at the time of the subject's final ¹⁸ F-AV-1451-A05 study visit and will include safety labs (may be collected any time prior to ¹⁸ F-AV-1451 Injection), ECG, and collection of updated medical history and concomitant medications if not collected within last 30 days. An MRI, including both volumetric and standard clinical sequences will be conducted prior to the subject's ¹⁸ F-AV-1451 PET imaging session. Subjects		

Sponsor: Avid Radiopharmaceuticals, Inc.	Name of Compound: ¹⁸ F-AV-1451([F-18]T807)	Active Ingredient(s): 7-(6-[F-18]fluoropyridin-3-yl)-5H-pyrido[4,3-b]indole
who qualify for the study will return to the clinic within 30 days of the screening visit for an ¹⁸ F-AV-1451 PET imaging session.		

Assessments and Endpoints:
 
Each subject will have a screening visit(s), an MRI visit, an ¹⁸F-AV-1451 PET imaging visit, and a follow-up phone call after the imaging visit.
 
¹⁸F-AV-1451 PET Imaging Session:
 
For the ¹⁸F-AV-1451 PET imaging session, subjects will receive a single IV bolus injection target dose of 370 MBq (10 mCi) of ¹⁸F-AV-1451. At approximately 80 minutes post dose, a continuous 20-minute brain scan (4 acquisitions of 5-minute duration) will be obtained.
 
Adverse events will be monitored continuously during the imaging session. Subjects who experience any adverse event during an imaging session will not be discharged until the event has resolved or stabilized.
 
A follow-up phone call to the subject, or designated decision maker, will be conducted within 2 to 3 business days of the imaging day, but not before 48 hours post-injection, to confirm subject well-being and to collect information about any new adverse events. If both of these days are not business days, the follow-up phone call can occur the following business day. Additional assessments that will be performed at each visit are detailed in Section 7.1.
		

Statistical Methods:
 
Descriptive statistics will be used to summarize the change in AV-1451 from A05 baseline (Change From Baseline; CFB) for the AV-1451 SUVR from the combination region and individual sub-regions. Analysis of covariance (ANCOVA) adjusting for baseline AV-1451 SUVR level and age will be applied to compare the least square (LS) mean tau CFB by clinical diagnosis groups (MCI vs. AD), amyloid status (AB+ vs. AB-) and the interaction of these two factors. The relationship between AV-1451 SUVR CFB and cognitive function assessments CFB will also be explored using ANCOVA models.
		

TABLE OF CONTENTS

1.	INTRODUCTION	8
2.	TRIAL OBJECTIVES	11
3.	SPONSOR, INVESTIGATOR(S) AND OTHER PARTICIPANTS	11
4.	TEST DRUG AND CONTROL AGENTS	12
4.1.	Descriptive Name: ¹⁸ F AV-1451	12
4.2.	Radioactive Labeling	12
4.3.	Decay Characteristics	12
4.4.	Formulation and Dose ¹⁸ F-AV-1451 Injection	12
4.5.	Packaging ¹⁸ F-AV-1451 Injection	13
4.6.	Storage and Handling ¹⁸ F-AV-1451 Injection	13
5.	INVESTIGATIONAL PLAN	13
5.1.	Overall Design and Plan of Trial	13
5.2.	Planned Dosage and Duration of Treatment	14
5.2.1.	Dosage and Administration	14
5.2.2.	Rationale for Dosages	14
5.3.	Selection of Subjects	14
5.3.1.	Inclusion Criteria	14
5.3.2.	Exclusion Criteria	15
5.4.	Prior and Concomitant Therapy	15
5.5.	Removal of Subjects from Trial	15
5.6.	Premature Termination of Trial/Closure of Center	16
6.	WARNINGS/PRECAUTIONS	16
7.	PROCEDURES AND METHODS	16
7.1.	Assessment Periods	16
7.1.1.	Screening Visit:	17
7.1.2.	MRI Visit:	17
7.1.3.	PET Imaging Visit:	17
7.2.	Observations and Measurements	18
7.3.	Protocol for Image Collection	19
7.4.	Good Clinical Practice and Monitoring	19
7.5.	Informed Consent and Subject Information	19

7.6. Documentation..... 20

7.7. Adverse Events (AE) 20

7.7.1. Adverse Event Monitoring 21

7.7.2. Adverse Event Definitions..... 21

7.7.3. Adverse Event Documentation 23

7.7.4. Reporting of Serious Adverse Events..... 23

8. STATISTICAL ANALYSIS 23

8.1. General Statistical Considerations 23

8.1.1. Sample Size Estimation 24

8.2. Efficacy Analysis..... 24

8.3. Safety Analysis 24

8.4. ¹⁸F-AV-1451 Image Analysis 25

9. USE OF DATA AND PUBLICATION 25

10. INVESTIGATOR’S REGULATORY OBLIGATIONS 26

10.1. Institutional Review Board (IRB)..... 26

10.2. Informed Consent 26

10.3. Protocol Adherence 26

10.4. Documents Necessary for Initiation of the Trial 26

10.5. Investigational Product Control..... 27

10.6. Data Collection 27

10.7. Adverse Events 27

10.8. Records Retention..... 28

11. APPENDICES 29

11.1. References..... 29

11.2. Trial Flow Chart 31

ABBREVIATIONS AND DEFINITIONS

Aβ	Beta amyloid
AD	Alzheimer's disease
Adverse Event (AE)	Any untoward medical occurrence in a subject or clinical investigation subject administered a pharmaceutical product and that does not necessarily have a causal relationship with this treatment.
Audit	A systematic and independent examination of the trial-related activities and documents to determine whether the evaluated trial-related activities were conducted, and the data were recorded, analyzed, and accurately reported according to the protocol, applicable standard operating procedures (SOPs), good clinical practice (GCP), and the applicable regulatory requirement(s).
Case Report Form (CRF) and electronic Case Report Form (eCRF)	A printed or electronic form for recording study participants' data during a clinical study, as required by the protocol.
CNS	Central Nervous System
CRO	Contract Research Organization: A person or organization (commercial, academic, or other) contracted by the sponsor to perform one or more of the sponsor's trial-related duties and functions.
CT	Computed Tomography
Efficacy	Efficacy is the ability of a treatment to achieve a beneficial intended result.
FDA	US Food and Drug Administration
FDG	¹⁸ F - Fluorodeoxyglucose
GCP	Good Clinical Practice
ICH	International Conference on Harmonization
Institutional Review Board	A board or committee (institutional, regional, or national) composed of medical and nonmedical members whose responsibility is to verify that

/Independent Ethics Committee	the safety, welfare and human rights of the subjects participating in a clinical study are protected.
Investigator	A person responsible for the conduct of the clinical trial at a trial site. If a trial is conducted by a team of individuals at a trial site, the investigator is the responsible leader of the team and may be called the principal investigator.
IV	Intravenous
K_a	Dissociation Constant
MBq	Megabecquerel
mCi	Millicurie
MCI	Mild Cognitive Impairment
MHD	Maximum Human Dose
MRI	Magnetic Resonance Imaging
NOAEL	No Observable Adverse Effect Level
PET	Positron Emission Tomography
SUV_r	Standard Uptake Value Ratio

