8.1.1. Sample Size Estimation

This study is estimated to enroll about 100 subjects from A05 confirmatory arm. Current analyses with A05 exploratory arm data showed that for subjects met A05 confirmatory arm enrollment criteria (MCI or demented, MMSE between 20 and 27), AV1451 SUVR on average changed 0.0527 (SD=0.0970) for amyloid positive subjects at 9 months follow up. Assume a similar amyloid positivity to A05 exploratory arm (~60%), and assume the change of AV1451 SUVR is linear, this study is expected to have approximately 60 amyloid positive subjects and the mean change of AV1451 SUVR is expected to be 0.105, with a 95% confidence interval (0.0635, 0.1473).

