5. CHANGES FROM PROTOCOL

The following changes from the protocol are reflected in this SAP.

- With continued development and accumulated knowledge, Multi-Block Barycentric Discriminant Analysis (MUBADA) SUVr instead of Combination ROI, will be used as the global measurement of tau deposition.

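### The synopsis plans about 160 enrolled subjects and the sample-size sections about 100; separately, the 95% interval printed there matches a 90% interval for 60 amyloid-positive subjects

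*Protocol*

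**What the plan says.** The synopsis of the protocol gives "Planned number of subjects (Enrolled): Approximately 160". Section 8.1.1 of the same protocol says "This study is estimated to enroll about 100 subjects from A05 confirmatory arm", and SAP 3.4 repeats that figure.

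Section 8.1.1 then builds its precision statement:

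- From the A05 exploratory arm: "AV1451 SUVR on average changed 0.0527 (SD=0.0970) for amyloid positive subjects at 9 months follow up".
- The extrapolation: "Assume a similar amyloid positivity to A05 exploratory arm (~60%), and assume the change of AV1451 SUVR is linear".
- The resulting count: "this study is expected to have approximately 60 amyloid positive subjects".
- The resulting estimate: "the mean change of AV1451 SUVR is expected to be 0.105, with a 95% confidence interval (0.0635, 0.1473".

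SAP 3.4 carries the same figures, with only the tracer's name changed. SAP 5 opens with "The following changes from the protocol are reflected in this SAP" and lists one item, the switch to MUBADA as the global tau measure.

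**The concern.** Both 160 and 100 are described as enrolment, so a distinction between screened and evaluable subjects does not explain the gap. A difference of 60 is also too large for the word approximately to absorb. Neither document gives an attrition rate, an uptake rate from A05, or a ceiling that would link them. A site or ethics board cannot tell whether about 100 or about 160 people are to receive the tracer.

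The interval is a second and independent matter. Protocol 8.1.1 and SAP 3.4 contain the plan's only precision statement, and there is no power calculation alongside it. If the label is wrong, that statement claims more precision than the design delivers. Correcting the enrolment figure would not correct the label, nor the reverse.

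**Working it through.** **Inputs.** Protocol 8.1.1 and SAP 3.4 give the 9-month mean change (0.0527), its SD (0.0970), amyloid positivity (60%), enrolment (100), and the printed limits (0.0635, 0.1473). The synopsis gives 160. The follow-up SD is not stated.

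**Amyloid-positive count.**

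- 0.6 × 100 = 60, which reproduces the plan.
- 0.6 × 160 = 96, which does not.

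**Expected mean.** SAP 6.2 uses 18-month A05 cognitive data, so linear change from 9 months means a factor of 2: 2 × 0.0527 = 0.1054. This agrees with the printed 0.105 and with the midpoint of the printed limits, (0.0635 + 0.1473)/2 = 0.1054.

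**Printed half-width.** (0.1473 − 0.0635)/2 = 0.0419.

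**Reproducing the interval.** The formula is mean ± t × SD/√n. If each subject's change is linear, the SD doubles with the mean: 2 × 0.0970 = 0.194. With n = 60, the standard error is 0.194/√60 = 0.02505.

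- 90%: t(0.95, 59) × 0.02505 = 0.04185, giving (0.06355, 0.14725). Before rounding to five places the limits are 0.063547 and 0.147253, which round to the printed 0.0635 and 0.1473. The confidence level implied by the printed half-width is 90.04%.
- 95%: t(0.975, 59) × 0.02505 = 0.0501, giving (0.0553, 0.1555). Relative width: 0.0501/0.0419 = 1.20.

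**Does 160 explain the interval?** With n = 96 and SD 0.194:

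- 95%: half-width 0.0393, giving (0.0661, 0.1447).
- 90%: half-width 0.0329, giving (0.0725, 0.1383).

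Neither matches.

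**Other values of the unstated SD.** 95% t half-widths, to compare with the printed 0.0419:

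| Follow-up SD | n = 60 | n = 96 |
|---|---|---|
| 0.0970 (unchanged) | 0.0251 | 0.0197 |
| 0.1372 (× √2) | 0.0354 | 0.0278 |
| 0.194 (× 2) | 0.0501 | 0.0393 |

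None of the six equals 0.0419. The ratio of the n = 96 to the n = 60 half-width is the same in every row because the SD cancels: 0.0393/0.0501 = 0.78, so about 22% narrower.

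**Other values of n at 95%.** With SD 0.194 the closest t interval is at n = 85, giving (0.0636, 0.1472). That would need 85/0.6 ≈ 142 enrolled, which matches neither 100 nor 160. With SD 0.1372 an approximate match needs n of about 41 to 44, and with SD 0.0970 about 23. The plan gives none of these numbers.

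**The case against.** The strongest objection is to the interval. The linearity assumption is used to extrapolate the mean and says nothing explicit about the SD. Exact doubling implies no scan-to-scan noise. The table tests three SDs, and the printed half-width of 0.0419 lies between the second and third entries for n = 60. An SD of 0.1621, which is 1.67 × 0.0970, gives t(0.975, 59) × 0.1621/√60 = 0.0419 and hence the printed limits at 95%. Such an SD could arise if about 60% of the 9-month variance were between-subject slope, growing fourfold over a doubled interval, and 40% were constant noise: √(4 × 0.6 + 0.4) = 1.67. The documents neither state nor exclude this. It is therefore correct that the 90% reading is an inference and that the table does not rule out every 95% reading. But the alternative needs an input that appears nowhere in the plan, while the 90% reading uses only the plan's own numbers and reproduces both limits to four decimals.

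On enrolment, it is fair to say that SAP 5 had nothing to list, because SAP 3.4 agrees with Protocol 8.1.1. The conflict lies between the protocol's synopsis and its body. SAP 5 shows only that the SAP does not resolve it.

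It is also true that the consequences are modest. This is an open-label, single-injection roll-over study whose numbers depend partly on uptake from A05, with no interim analysis or randomization tied to the sample size.

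**Conclusion.** Both points hold.

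The enrolment conflict is plain on the text and needs no assumption: 160 against 100 enrolled, and 96 against 60 amyloid-positive subjects at the plan's own rate. The sample-size reasoning rests on 100.

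The interval is, with high probability, a 90% interval labelled 95%. That identification assumes that the follow-up SD is twice the 9-month SD. On that assumption the 95% interval for 60 subjects is about 20% wider than printed. Without a stated SD, the printed interval cannot be verified at all, which is itself a gap. The agreement at n = 60 also supports 100 as the working enrolment figure.

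The effect on conclusions is limited. The corrected 95% interval still excludes zero, and no hypothesis test, analysis population or alpha level changes. It should be fixed because it affects the stated size of the study and its only statement of precision, in two documents.

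**What to change.** 1. Give one planned enrolment in the synopsis, Protocol 8.1.1 and SAP 3.4. If 160 is a ceiling and 100 the expected number, say so in each place.
2. In Protocol 8.1.1 and SAP 3.4, state the SD assumed at follow-up and how it was obtained from the 9-month value.
3. Then either relabel (0.0635, 0.1473) as a 90% interval, if the SD is 0.194 and n is 60, or print the 95% interval for the committed number. With SD 0.194 that is (0.0553, 0.1555) for 60 amyloid-positive subjects or (0.0661, 0.1447) for 96. With another SD, recompute.

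Item 1 and items 2 and 3 are independent, and both sets are needed. The cost is a change to one synopsis cell and to the wording of the two sample-size sections, with no added patients, visits or analyses.

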1. INTRODUCTION

Molecular imaging biomarkers have the potential to aid in the diagnosis of patients with cognitive impairment who are being evaluated for Alzheimer's disease (AD) (Dubois, 2010; McKhann, 2011). Positron emission tomography (PET) ligands such as florbetapir F 18 (Wong, 2010) may provide a minimally invasive estimate of cortical beta amyloid (A β) neuritic plaque deposition, a hallmark pathology, and a required element for the evaluation of AD neuropathologic diagnosis (Hyman 2012). Multiple studies comparing amyloid PET scans to histopathologic assessment of amyloid burden, in subjects for whom biopsy samples were available or who came to autopsy after receiving a PET amyloid scan, support the relationship between PET amyloid imaging results and cortical neuritic plaque density (Clark 2011, 2012; Leinonen, 2008; Sojkova, 2011; Kantarci, 2011; Burack, 2010). The largest of these studies (Clark 2012) demonstrated a high sensitivity and specificity for florbetapir PET to discriminate subjects with subsequent autopsy findings of no or sparse neuritic plaques (amyloid negative) from those with moderate to frequent plaques (amyloid positive).

The ability to image brain amyloid with compounds such as florbetapir is an important advance for diagnosis of neurological disease. An amyloid negative florbetapir PET scan indicates the absence of a hallmark pathology and is inconsistent with a diagnosis of AD. However, because amyloid is believed to accumulate very early in the disease process (Jack et al., 2010) and may be present in other diseases or in clinically normal elderly subjects (Sperling et al. 2011; Price and Morris, 1999), the density or distribution of amyloid in subjects with a positive scan is not associated with Alzheimer's disease severity, has not been established to predict rate of future deterioration and has not been established as a tool to predict or monitor response to therapy.

In contrast to A β neuritic plaques, the density and distribution of phosphorylated tau, aggregated in neurofibrillary tangles, increases with AD-related cognitive impairment and correlates with neurodegeneration (Dickson et al., 1997; Duyckaerts et al., 1987). Thus, a PET imaging agent that binds to phosphorylated tau has potential application as a biomarker for disease severity/neurodegeneration and may be useful both for selecting patients for therapy and for monitoring disease progression in therapeutic trials.

¹⁸F-AV-1451 (originally named [F-18]T807 by Siemens Molecular Imaging Biomarker Research group) has been developed as a positron emitting radiopharmaceutical for *in vivo* imaging of tau protein aggregates (Xia et al., 2013). Autoradiography results using tissue sections from human brains showed a strong signal in the grey matter of cortical slices from tau positive brains but weak or no binding in tau negative, A β positive, or tau and A β negative tissue. Scatchard analysis based on this heterogeneous autoradiography assay yielded an estimated K_d of 15nM. A saturation binding experiment using purified Paired Helical Fragment Tau isolated brains of AD patients yielded a K_d value of 0.54 nM.

AV-1451 was assessed in competitive binding assays against a panel of 72 of the most common central nervous system (CNS) targets and no clinically relevant inhibition was seen. AV-1451 was positive in the *in vitro* hERG assay; however, *in vivo* cardiovascular safety pharmacology assessments in dogs showed no evidence of QT prolongation at

doses up to 50x the intended maximum human dose (MHD). Nonetheless, until sufficient human cardiovascular safety data are available, initial clinical studies will exclude subjects with a history of risk factors for Torsades de Pointes and subjects taking drugs known to prolong the QT interval.

[figure not shown]
In vivo safety pharmacology studies were also conducted in rats to determine potential effects on the CNS and respiratory systems. In these studies no clinically relevant effects were reported at doses exceeding 100x the intended MHD. Additionally, non-radioactive AV-1451 has been tested in single and repeat-dose toxicology studies in rat and dog. In each of these studies the no observable adverse effect levels (NOAELs) were the highest doses tested (150x MHD for single, 50x MHD for repeat).

Potential genotoxicity of non-radioactive AV-1451 was tested in both *in vitro* and *in vivo* assays. In the *in vitro* assays, AV-1451 tested positive for potential genotoxicity. However, in the *in vivo* rat micronucleus assay at doses up to 750x MHD (scaled allometrically), AV-1451 showed no evidence of genotoxicity. The different results in the *in vitro* genotoxicity assays and the *in vivo* micronucleus study are likely related to differences in the exposure conditions encountered by the target cells in the different test systems. *In vivo*, AV-1451 is cleared rapidly; however, the *in vitro* experiments employ static, prolonged exposure of cells to high concentrations of the test article. While the *in vitro* data show the potential for genotoxicity, the *in vivo* data provide assurance that genotoxicity is unlikely to occur at clinically-relevant doses for human diagnostic studies.

Three human clinical studies have been completed with ¹⁸F-AV-1451. A total of 59 subjects have been exposed to ¹⁸F-AV-1451 in these studies. The following side effects have been reported in clinical studies: diarrhea, headache, and altered taste. All reported events were mild in intensity and all subjects recovered from these events.

Evaluation of the PET images from completed studies demonstrates little focal cortical retention of ¹⁸F-AV-1451 in either young cognitively normal (YCN) or older cognitively normal (OCN) subjects known to be amyloid negative (florbetapir PET SUVR <1.10; [Figure 1](#) Panels A and B). However, OCN subjects frequently demonstrated retention in the mesial temporal lobes and some OCN subjects also demonstrated retention in the brainstem or striatum ([Figure 1](#) Panel B). In MCI and AD subjects, retention appeared to spread from mesial temporal lobes to isocortical areas ([Figure 1](#) Panels C-F). The pattern of ¹⁸F-AV-1451 distribution seen on PET imaging, across subjects with various levels of impairment, paralleled the pattern reported in the classic autopsy series of older persons and subsequently used to define the Braak stage (Braak and Braak, 1991). Two clinically diagnosed AD subjects that were found to be amyloid negative on a florbetapir PET scan were the exception to this pattern, as their scans were similar to clinically normal elder controls and showed no cortical ¹⁸F-AV-1451 retention ([Figure 1](#) Panel G).

Figure 1: Representative ¹⁸F-AV-1451 PET Scans

Human dosimetry has been obtained in nine subjects. Generally, the radiotracer distribution was consistent among the subjects and showed rapid hepatobiliary clearance. There were three organs that received estimated doses higher than 0.05 mSv/MBq: the upper large intestinal wall (0.0955 ± 0.0134 mSv/MBq), the small intestine (0.0845 ± 0.0118 mSv/MBq) and the liver (0.0572 ± 0.00803 mSv/MBq). The Effective Dose was 0.0235 ± 0.0016 mSv/MBq. This results in an estimated Effective Dose of 8.70 mSv for an anticipated 370 MBq (10 mCi) injection and is comparable to the effective dose of approved ¹⁸F-labeled compounds such as fluorodeoxyglucose (FDG) and florbetapir F 18 injection.

The overarching goal of this protocol is to further investigate the spectrum of PET imaging results with ¹⁸F -AV-1451 in patients with cognitive decline. To accomplish this goal, the protocol will investigate longitudinal ¹⁸F-AV-1451 results in patients with cognitive complaints ranging from mild cognitive impairment (MCI) to mild and moderate Alzheimer's disease (AD).

